#### 1 ABBREVIATIONS

ECRF – Electronic case report form

ED – Emergency department

EHR - Electronic health record

EP – Emergency physician

ESP - Erector spinae plane

ESPB – Erector spinae plane block

G6PD – Glucose-6-phosphate dehydrogenase deficiency

HIPAA - Health insurance portability and accountability act

POCUS - Point of care ultrasound

U-M - University of Michigan

US – Ultrasound

UGRA - Ultrasound guided regional anesthesia

#### 2 STUDY SUMMARY

#### 2.1 Title

Erector spinae plane block for renal colic

# 2.2 Primary Objective

Determine the efficacy of the erector spinae plane block (ESPB) performed by emergency physicians (EPs) for the treatment of pain related to uncomplicated urolithiasis

# 2.3 Secondary Objectives

- Determine the effect of ESPB on emergency department (ED) operations metrics (disposition, length of stay, return to ED)
- Determine the effect of ESPB on use of opioid medications in the ED and during the follow up period
- Estimate rate of complications for ESPB when performed by EPs

# 2.4 Hypothesis

EP performed ESPB will reduce the proportion of patients receiving a second parenteral medication to treat pain in the ED

# 2.5 Study Design

Single site two-stage open label phase 2 clinical trial with one treatment arm and one external control arm

#### 2.6 Inclusion Criteria

- Adult emergency department patient presenting with pain due to uncomplicated urolithiasis
- Imaging confirmation of urolithiasis on the index encounter or prior encounter within 7 days
- Patient received one dose of parenteral pain medication in the ED

#### 2.7 Exclusion Criteria

- Pregnancy or breastfeeding
- Prisoner or incarcerated individual
- Therapeutic anticoagulation or coagulopathy
- Active treatment for urinary tract infection (either acute infection or chronic therapy)
- Prior spinal surgery in the thoracic region
- Allergy to local anesthetic
- Soft tissue infection overlying the injection site
- Covid positive
- Inability to communicate verbally or read/write in English
- Currently taking strong CYP1A2 inhibitor (fluvoxamine, amiodarone, fluoroquinolones, etc.)
- Glucose-6-phosphate dehydrogenase deficiency (G6PD)

#### 2.8 Primary outcome

Proportion of patients that receive a second parenteral medication for pain related to urolithiasis

# 2.9 Secondary and exploratory outcomes

 Difference in visual analog scale pain (1-10) from prior to procedure to first pain assessment after 60 minutes from completion of ESPB as assessed by bedside nurse

- ED operational metrics admission to hospital, rate of 72-hour return to ED and length of stay
- Opioid pain medication usage measured in intravenous morphine equivalents and proportion of patients that receive a prescription for opioid pain medication
- Survey follow-up administered online with/without telephone assistance at 1, 7 and 30 days from initial ED visit (days 1, 7 are optional and on day 30 pain medication use questions are optional)
- Frequency of prespecified complications related to ESPB

# 2.10 Sample Size

- This study is a two-stage trial with one planned interim analysis for futility
- Based on the prior 30-month time period (as of May 2022), 572 out of 1071 patients (53.4%) presenting to the ED and meeting the inclusion criteria did not require a 2nd parenteral pain medication during the ED encounter. Thus, we estimate a baseline response rate of 55%.
- Prior work by Nobel et al.¹and Aydin et al.² suggests that no patient will require a second dose of any pain medication after ESPB, but we estimate a conservative response rate of 75% for treatment with ESPB.
- Using Simon's optimal two-stage design with these parameters and  $\alpha$  = 0.05,  $\beta$  = 0.10, we estimate that 18 subjects will be required at the interim analysis and 54 subjects will be required to complete this study.
- Using a Bayesian two-stage design, where interim analysis is planned at one-third total enrollment and a stopping rule if there is only a 10% probability of ESPB demonstrating a 75% response rate, we estimate that 45 total subjects (15 at interim analysis) will be required to achieve a 1.4% chance of stopping early and 95.2% chance of rejecting the null hypothesis.
- This study will aim to achieve a total enrollment of 60 subjects who receive ESPB to account for losses to follow up and withdrawals from the study. Up to 180 (3:1 ratio) historical controls will also be included in the study thus the total enrollment including both treatment and control patients is 240.

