#### 3.6 Outcomes

#### 3.6.1 Primary Outcome and rationale

The primary outcome will be the proportion of patients receiving a second parenteral pain medication in the ED after a single-shot ESPB is performed by a study investigator. We have reviewed historical data that suggests that the rate of response (percentage of patients that do not require a second parenteral pain medication) in patients with urolithiasis, and who receive a parenteral medication as the first analgesic in the ED (approximately 70% of all kidney stone patients), ranges from 47 to 57% for the years 2020 – 2022. The average response rate is 53.4% during this period which is in line with historical trends prior to the Covid-19 pandemic.

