# 4.4 Selection of external control patients

External control patients will be selected from a population of patients meeting the following criteria: 1) adult ED patient with the diagnosis of uncomplicated kidney stones; 2) received at least one dose of parenteral medication while in the ED; 3) presentation to the ED between 7/1/2021 and the study start date. From this population, propensity score matched control patients will be selected at a ratio of 3 controls to 1 ESPB patient. External control population patients are not active patients in this study and analysis of their data will be secondary use of data collected during routine care. To provide valid comparison between control patients and ESPB patients, we will compare pain scores obtained by the treatment team (bedside nurse). For all other primary and secondary outcomes, data collection utilizes EHR query that does not require prospective data collection. Please see the data collection section of this protocol for further details.

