# **5 STUDY PROCEDURES**

# 5.1 Study Design and Workflow

This study is designed to be a pragmatic, single treatment arm two-stage trial that investigates the efficacy of the ESPB to treat pain related to kidney stones in ED patients in comparison to an external control group. The overall study workflow is diagrammed in Figure 1B and Figure 1C. We plan to have our study team members screen for patients based on the availability of the ED ultrasound team - a clinical care team that performs diagnostic and ultrasound guided procedures at the bedside in the ED. Eligible patients will be approached by a study investigator (the proceduralist) who will obtain informed consent and perform the ESPB. The investigator will also collect data from the patient 1 hour after performing the procedure. Follow up assessments using a web-based survey are an optional sub-study. Participants who do not elect to participate in the optional sub-study will receive a telephone call at day 30 to assess only for adverse events. Study participation will be complete after final follow up assessment.

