#### 7 DATA ANALYSIS PLAN

# 7.1 Descriptive analysis and statistical testing

The primary exposure of interest is performance of ESPB for uncomplicated renal colic in the ED. We will describe the center and spread for all collected variables. Additionally, we will compare data from participants to historical control patients whose data is collected secondarily from query to the EHR. Continuous variables will be described by medians with interquartile ranges and differences will be assessed by two-sample t-test or Wilcoxon's rank sum test depending on distribution. Categorical variables will be described by counts with proportions and differences assessed using the Chi-squared test or Fisher's exact test where appropriate. An alpha = 0.05 will be considered the level of significance in all analyses.

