# 7.2 Primary analysis

Our primary analysis will evaluate the proportion of patients receiving ESPB who require a second parenteral pain medication. This outcome will be compared to external control patients who are selected using propensity score matching at a ratio of 3:1. The propensity score model will include the following variables: age, gender, triage acuity level (ESI score), first ED pain score assessed by nursing, Charlson Comorbidity Index, chronic and initial pain medication type. Data for this outcome will be collected via EHR query as above.

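### The 90% and 95.2% in section 2.10 are single-arm figures; the matched-control primary analysis has no stated power or sidedness, and its power is about 78% two-sided or 85% one-sided

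*Combined protocol and SAP*

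**What the plan says.** Section 2.10 is the plan's only sizing rationale, and it uses two designs.

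- **Simon's optimal two-stage design:** baseline response 55%, ESPB response 75%, alpha 0.05, beta 0.10. The result is "we estimate that 18 subjects will be required at the interim analysis and 54 subjects will be required to complete this study".
- **Bayesian two-stage design:** 45 patients, 15 of them at the interim, with a "95.2% chance of rejecting the null hypothesis".

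The section then sets a target of 60 ESPB patients, to allow for losses and withdrawals, and at most 180 historical controls.

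The rest of the plan describes a comparison of two groups. Section 2.5 has "one treatment arm and one external control arm". Section 5.1 investigates efficacy "in comparison to an external control group". Section 4.4 says "propensity score matched control patients will be selected at a ratio of 3 controls to 1 ESPB patient". Section 7.2, headed as the primary analysis, says of the second-medication outcome: "This outcome will be compared to external control patients who are selected using propensity score matching at a ratio of 3:1".

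Section 7.2 names no test. The general section 7.1 offers chi-squared or Fisher's exact test for categorical data and adds: "An alpha = 0.05 will be considered the level of significance in all analyses". It does not say one-sided or two-sided. The hypothesis in 2.4 is directional. From the Simon design, section 7 keeps only the first-stage futility stop (7.3).

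**The concern.** A single-arm design treats the 55% comparator as known. The analysis in 7.2 estimates it from at most 180 matched controls, which adds variance. The Simon alpha of 0.05 is one-sided, whereas a chi-square test as ordinarily run is two-sided. Both differences lower power, so a reader who takes 90% or 95.2% as the power of the primary analysis will be misled. A null result would be judged against power that the test does not have.

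The open sidedness is a separate gap. If it is not fixed beforehand, it could be chosen after the data are seen.

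**Working it through.** **Inputs.** Control response 55%, or 53.4% as observed (572/1071); ESPB response 75%; alpha 0.05, beta 0.10; 60 ESPB patients and up to 180 controls (all 2.10). Chi-square or Fisher (7.1). Stop if 8 or more of the first 18 receive a second parenteral medication, i.e. 10 or fewer responders (7.3). Yearly control response "ranges from 47 to 57" percent (3.6.1).

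**1. Reproduce the plan's figure.** An exact binomial search for Simon's optimal design gives: stop at 10 or fewer responders of 18; declare success above 35 of 54. Exact one-sided alpha is 0.0477 and power 0.9007. So 18/54 is right for its own design, and its first-stage boundary is the stop in 7.3. The final boundary (more than 35 of 54) appears nowhere in the plan. The 95.2% could not be reproduced, because the prior and final decision threshold are not given.

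**2. Normal approximation for the two-group comparison, 60 v 180, no stop.**

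- Pooled response: (60 × 0.75 + 180 × 0.55)/240 = (45 + 99)/240 = 0.60
- SE under the null: √[0.60 × 0.40 × (1/60 + 1/180)] = 0.0730
- SE under the alternative: √[0.75 × 0.25/60 + 0.55 × 0.45/180] = √(0.003125 + 0.001375) = 0.0671
- Two-sided power: Φ[(0.20 − 1.960 × 0.0730)/0.0671] = Φ(0.85) = 80.2%
- One-sided power: Φ[(0.20 − 1.645 × 0.0730)/0.0671] = Φ(1.19) = 88.3%

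Sampling the controls adds 0.001375/0.003125 = 44% to the variance of the ESPB proportion alone.

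**3. Exact enumeration.** Both binomials are enumerated with the pooled, uncorrected chi-square. Without the stop, power is 80.7% two-sided and 88.4% one-sided. The stop ends 5.7% of trials when the true response is 75%, so power with it cannot exceed 94.3%. With the stop and 75% ESPB response:

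| Sizes | Control response | Two-sided | One-sided |
|---|---|---|---|
| 60 v 180 | 55% | 78.1% | 85.0% |
| 60 v 180 | 53.4% | 83.1% | 88.3% |
| 60 v 180 | 47% | 92.6% | 93.6% |
| 60 v 180 | 57% | 70.3% | 79.3% |
| 54 v 162 | 55% | 74.0% | 82.4% |
| 54 v 162 | 53.4% | 79.6% | 86.2% |
| 60 v 120 | 55% | 73.4% | 81.4% |

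Sixty is the more relevant ESPB size, because 7.2 takes the outcome from the EHR and loss to follow-up should matter little. The 60 v 120 row is included because 180 is a ceiling.

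**4. Choice of test, 60 v 180 at 55%.** Fisher: 76.9% two-sided with the usual p-value (74.3% if the one-sided p is doubled), 82.1% one-sided. Continuity-corrected chi-square: 73.6% / 82.0%.

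**5. Matching.** The documents give no within-set correlation, so a range is assumed. In 60,000 simulated trials per case (60 sets of 1:3, Mantel-Haenszel test stratified by set, stop included, 55% controls), two-sided / one-sided power is 77.5% / 84.8% at correlation 0, 81.1% / 87.3% at 0.1 and 84.2% / 89.0% at 0.2.

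**6. What sidedness decides.** At 60 v 180 and 55%, it changes the verdict in 0.8503 − 0.7814 = 6.9% of trials. Against 99/180 controls:

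| ESPB responders | One-sided p | Two-sided p |
|---|---|---|
| 40/60 | 0.056 | 0.113 |
| 41/60 | 0.035 | 0.070 |
| 42/60 | 0.020 | 0.041 |

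The verdict is open only at 41 of 60.

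**The case against.** The strongest reply is that the plan states no success criterion. Section 7.2 mentions the ESPB proportion before the comparison, the trial is described as two-stage, and 7.3 uses the Simon stop. The sponsor could therefore state the Simon final boundary as the decision rule and keep the matched comparison as supporting, in which case 90% would be right. That repair is coherent, but it would replace the primary analysis that 7.2 describes, and the boundary it needs is not in the plan.

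Other points have partial force:

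- **Control rate.** 55% is rounded up from 53.4%, at which two-sided power is 83%. That is still below 90%.
- **Effect size.** The plan calls 75% conservative. At 80% v 55%, two-sided power is 92% (54 v 162) to 94% (60 v 180). This stands and limits the practical harm.
- **Sidedness.** A chi-square test is normally two-sided, and a directional hypothesis does not change that. This is fair, but one word would settle it, and the two readings differ by about 7 percentage points of power.
- **Assumed test.** The headline uses an uncorrected, unmatched chi-square, which the plan does not specify. Fisher or a continuity correction lowers power; a test that uses the matched sets may raise it to about 81–84% two-sided under the assumed correlations.

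**Conclusion.** The concern holds. The sample-size section describes single-arm tests, and no power is given for the comparison that 7.2 makes primary. At the planned 60 v 180 with 75% v 55% response, that comparison has about 78% power two-sided or 85% one-sided. This assumes independent groups, a full 3:1 match, an uncorrected chi-square at 0.05 and the futility stop in 7.3. Over the 47–57% yearly control range and both ESPB sizes (54 and 60), power runs from about 66% to 94%, depending also on sidedness.

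This should be fixed, but its reach is limited. The 18/54 calculation is not an error, the futility rule stands, and no patient-level decision changes. Two-sided power of 78–83% is not a failed design for a phase 2 trial; the fault is that the stated figures belong to different tests.

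**What to change.** **Section 2.10.** State that 18/54 with beta = 0.10, and 45 patients with 95.2%, are operating figures of single-arm designs, and that the Simon design is the basis of the futility rule in 7.3. Then give power for the 7.2 comparison with its assumptions: 60 ESPB patients, 180 controls, 75% v 55% response, two-sided uncorrected chi-square at 0.05, independent groups, futility stop included. Power is about 78%, or 83% if controls respond at 53.4%. Add that 180 is a maximum and that 120 controls would give about 73%. If a one-sided test is intended, the three figures are 85%, 88% and 81%.

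**Section 7.2.** Name the test, including any continuity correction, and its sidedness. Name the matched comparison as the sole decision test. If the chosen test differs from the one above, or accounts for the matched sets, say so and give power on that basis.

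**Cost.** Wording in two sections. No added patients or data, and the primary analysis in 7.2 stays as planned. The downside is that the stated power falls below 90%.

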# 7.3 Interim analysis

Both a Simon's optimal two-stage and Bayesian two-stage design were used to estimate sample size (see section 2.10 above) with the Simon's design yielding a slightly larger group for interim analysis (18 patients). Thus, we will plan to perform an interim analysis at 18 recruited patients who have received the ESPB and if 8 or more patients receive a second parenteral pain medication then the study will be ended for futility.

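### Section 2.10 credits a 45-patient Bayesian design with 95.2% power, which 45 patients can reach only at an undisclosed type I error of about 12%

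*Combined protocol and SAP*

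**What the plan says.** Section 2.10 takes a baseline response rate of 55%, rounded from an observed 572 of 1071 (53.4%), and a target of 75% with the block. It gives two sizing calculations one after the other.

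- **Simon's optimal two-stage design**, with alpha 0.05 and beta 0.10: 18 patients at the interim and 54 in all.
- **A Bayesian two-stage design**, with the interim at one third of enrolment and "a stopping rule if there is only a 10% probability of ESPB demonstrating a 75% response rate". The plan says that 45 patients, 15 at the interim, "will be required to achieve a 1.4% chance of stopping early and 95.2% chance of rejecting the null hypothesis".

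The Bayesian item gives no alpha, no prior and no criterion for success at the end. Section 7.1 says: "An alpha = 0.05 will be considered the level of significance in all analyses". Section 7.3 says: "Both a Simon's optimal two-stage and Bayesian two-stage design were used to estimate sample size". It then takes the interim at 18 patients because that is the larger of the two, and stops for futility if 8 or more of the 18 receive a second parenteral pain medication. The enrolment target is 60.

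**The concern.** Read together, the two items say that 54 patients give 90% power and that 45 give 95%, for the same two response rates. Fewer patients cannot give more power unless something else has been relaxed. The only thing left to relax is the type I error, and the plan does not report it for the second design.

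A reader or an ethics board could therefore take the target of 60 to be well above what 95% power requires, and could take the risk of wrongly stopping for futility to be near 1%. The first belief does not hold at alpha 0.05. The second does not describe the interim rule that the trial will use.

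**Working it through.** **Inputs.** p0 = 0.55 and p1 = 0.75 (2.10); alpha = 0.05 (Simon item in 2.10, and 7.1); n = 45 with 15 at the interim (2.10); interim rule at 18 patients (7.3). The plan does not say whether alpha is one- or two-sided. I assume one-sided, as is usual for Simon's design, which is the choice more favourable to the plan. X is the number of responders, and all figures are exact binomial.

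**1. Reproduce the Simon figures.** A search at p0 = 0.55, p1 = 0.75, alpha 0.05 and beta 0.10 returns the stated 18 and 54: stop at 10 or fewer of 18, reject at 36 or more of 54. Type I error is 0.0477 and power 0.9007. Stopping at 10 or fewer responders of 18 is the same as 8 or more non-responders, which is the rule in 7.3.

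**2. What 45 patients can do in one stage.** Type I error = P(X ≥ r | 45, 0.55); power = P(X ≥ r | 45, 0.75).

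| Reject at | Type I error | Power |
|---|---|---|
| ≥29/45 | 0.130 | 0.961 |
| ≥30/45 | 0.076 | 0.925 |
| ≥31/45 | 0.041 | 0.867 |
| ≥32/45 | 0.020 | 0.784 |

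At alpha 0.05 the best non-randomised rule is ≥31/45, with 86.7% power. If alpha were two-sided (0.025 per side), the rule would be ≥32/45, with 78.4%.

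**3. Upper bound for any rule.** Any Bayesian criterion, with any prior and any interim look, is in the end a rejection region on at most 45 outcomes, so the Neyman–Pearson bound applies. Rejecting at ≥31 and, with probability g, at exactly 30 uses up alpha 0.05 when g = (0.05 − 0.0409)/0.0352 = 0.257. Power is then 0.8673 + 0.257 × 0.0574 = 0.882. The reverse calculation, for power 0.952: g at exactly 29 = (0.952 − 0.9247)/0.0358 = 0.762, so type I error is at least 0.0762 + 0.762 × 0.0540 = 0.117.

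**4. Two-stage rules, 15 then 45, stopping at ≤7/15.** Early stop at p = 0.75: P(X ≤ 7 | 15, 0.75) = 0.0173.

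| Reject at | Type I error, p0 = 0.55 | Type I error, p0 = 0.534 | Power |
|---|---|---|---|
| ≥29/45 | 0.124 | 0.085 | 0.950 |
| ≥30/45 | 0.074 | 0.048 | 0.917 |
| ≥31/45 | 0.040 | 0.025 | 0.862 |

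The first row is the closest match found to the stated 1.4% and 95.2%. Using the observed 53.4% as the null does not rescue the figure: the best rule within 0.05 then has 91.7% power with this stop, or 92.5% in one stage (≥30/45, type I error 0.0499).

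**5. What 95.2% would take.** At alpha 0.05 and 55% v 75%, about 62 patients in one stage (≥41/62: type I error 0.04999, power 0.957), or about 66 with an interim at one third.

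**6. The interim rule adopted in 7.3.** P(X ≤ 10 | 18, 0.75) = 0.057 and P(X ≤ 10 | 18, 0.55) = 0.609.

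**The case against.** The strongest reply is that the alpha is imported. In 2.10 it belongs to the Simon item, and in 7.1 it follows a list of two-sample tests. The Bayesian item claims no type I error, so 95.2% may be correct output for a design whose error is about 12%. That stands as far as it goes: the documents do not show a miscalculation. But a power quoted beside a design at alpha 0.05, in a plan that applies 0.05 to all analyses, will be read at that level unless the reader is told otherwise. Non-disclosure is the defect.

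A reader might go further and infer that the 1.4% early-stop figure is unattainable, or that it contradicts the 10% stopping rule. The documents support neither.

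- The early-stop chance does not depend on the final alpha, and stopping at ≤7/15 gives 1.7%.
- If the 10% rule is a posterior probability that the response rate exceeds 75%, a uniform prior stops at ≤9/15, which ends 14.8% of trials at a true 75%. If it is a predictive probability of final success (uniform prior, success at ≥29/45), that probability is 4.9% at 7/15 and 15.4% at 8/15, so the rule stops at exactly ≤7/15. The wording allows both readings and no prior is given.
- The remaining gap could be simulation error. If 1,000 runs are assumed, the standard errors are 0.41 points on 1.73% and 0.69 on 94.97%, so both stated figures lie within one standard error. With 10,000 runs, 1.4% would not fit. The run count is not given.

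It is also true that the interim size and the target of 60 follow the Simon design, so no boundary or patient number depends on the 45. That limits the importance of the point. It does not remove it, because 7.3 names this design as a basis for the sample size.

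**Conclusion.** The point holds for power. With 45 patients at 55% v 75% and one-sided alpha 0.05, power is at most 86.7% for a non-randomised rule (88.2% for any rule), against a stated 95.2%. The shortfall is 8.5 points, and the chance of missing a true effect is 13.3% rather than 4.8%. The stated pair is approximated only with a type I error of about 12% (8.5% if the null is 53.4%), roughly two and a half times the plan's level. The bound needs no assumption about the prior. It rests on p0 = 0.55, p1 = 0.75 and one-sided testing; two-sided testing widens the gap.

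Two further inferences should not be drawn. First, the planned enrolment is not shown to be wrong by this point. Second, the Simon figure of 90.1% is not the power of the trial's primary analysis. The documents adopt only the Simon interim boundary, while 7.2 compares block patients with 3:1 matched controls. By the normal approximation, ignoring matching, with 60 v 180 patients, 75% v 55% and two-sided 0.05, the pooled rate is 0.60. The standard errors are √(0.24 × (1/60 + 1/180)) = 0.0730 under the null and √(0.1875/60 + 0.2475/180) = 0.0671 under the alternative. Then z = (0.20 − 1.96 × 0.0730)/0.0671 = 0.85, which is about 80% power.

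**What to change.** - **Section 2.10.** Delete the 45-patient sentence. Otherwise restate it with its prior, its final success criterion, the meaning of the 10% rule (posterior or predictive) and its type I error. A correct statement would be that 45 patients, with 15 at the interim, give about 86% power at one-sided alpha 0.05, or about 95% power only at a type I error of about 12%.
- **Section 7.3.** Reword so that the two designs are not presented as equivalent. State the early-stop chances of the interim rule in use: 5.7% at a true 75% response and 60.9% at 55%.
- **If the Simon figures are quoted** (reject at 36 or more of 54, type I error 4.8%, power 90.1%), label them as the one-sample sizing design and not as the power of the matched-control analysis in 7.2.

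The cost is wording in two sections and a less favourable quoted power. The interim size, the stopping boundary and the enrolment of 60 stay as they are.
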